8.32 Places for submitting reports: IRB

8.4 Data Monitoring Committee (if applicable): Not Applicable

9.0 CLINICAL AND LABORATORY EVALUATIONS AND STUDY CALENDAR

See Appendix I

10.0 CRITERIA FOR EVALUATION AND ENDPOINT DEFINITIONS

Primary Outcome Measure

1. Peak plasma concentrations (C_{max})
2. Time taken to reach the maximum concentration (T_{max})
3. Area under the plasma concentration versus time curve (AUC)

Secondary Outcome Measure

1. Levels of serum inflammatory biomarkers
 - Changes in IL-6, IL-8, TNF- α , IL-1 β , C-reactive protein

11.0 SPECIAL INSTRUCTIONS:

Blood samples will be taken at baseline (0 h) and at 2, 4, 6, 8 hours and 1, 7, 28, 56 and 70 days after intervention. At each defined time points, 5 mL of venous blood will be collected in serum separator tubes (BD Vacutainer) with clot activator (39) to measure serum vitamin D₃ and 25(OH)D₃ concentrations. Samples will be handled with care to minimize sunlight exposure during the time of collection. Samples will be immediately placed on ice and stored in aliquots at -80 °C until analysis. Serum levels of vitamin D₃ and its metabolites will be determined using LC/MS-MS. Levels of inflammatory biomarkers will also be determined at each defined time points.

12.0 DATA COLLECTION AND MONITORING

Data will be collected on case report forms, which will be retained for the duration of the study. Data will include subject demographics, clinical characteristics, laboratory data, and results of pharmacokinetic analyses. Data will be coded and stored on a password protected electronic database.

13.0 STATISTICAL CONSIDERATIONS

13.1 Pharmacokinetic Analysis

Population pharmacokinetic analysis will be performed using the maximum likelihood estimation via the EM algorithm (MLEM) as implemented in ADAPT 5 (Biomedical Simulations Resource, University of Southern California). Multiple candidate models will be evaluated to identify the model that best describes the observed plasma concentration data for vitamin D3 and 25(OH)D3. The maximum concentration and time to maximum concentration will be determined from the observed data.

Patient demographics, clinical characteristics, and pharmacokinetic parameters will be summarized using descriptive statistics.

Differences in the pharmacokinetic parameters between non-CF controls and CF patients will be determined by non-parametric Wilcoxon-Mann Whitney test.

13.2 Comparison of mean serum and plasma concentrations of inflammatory markers at baseline and 10 weeks post intervention

Mean serum/plasma concentrations of inflammatory biomarkers will be compared between CF and non-CF, as well as within groups. Differences in the mean concentrations of inflammatory markers will be determined by non-parametric Wilcoxon-Mann Whitney test.

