review of pediatric CF patients, majority of patients (79%) rapidly and safely achieved and sustained optimal 25OHD levels over a 12 month period with a single high-dose oral vitamin D3 (300,000 IU – 600,000 IU), also known as stoss therapy (25). However, approximately 20% of patients still could not achieve levels above 30 ng/mL. Wide inter-individual variability in response to vitamin D treatment has been previously reported in non-CF population, suggesting that fixed-dose approach to replacement therapy may not be effective in improving 25(OH)D status in CF (30). Poor oral bioavailability of ergocalciferol has been demonstrated in CF patients (31), which suggests that CF patients may potentially exhibit low absorption of cholecalciferol. Therefore, based on the degree of malabsorption of vitamin D and basal vitamin D status, supplementation should be tailored to individuals. In order to optimize the treatment of deficiency in CF, kinetic disposition of vitamin D must be well understood. However, there are very few data currently available describing the kinetics of both vitamin D and 25-hydroxyvitamin D, and to the investigator's knowledge, no studies have yet characterized the pharmacokinetic disposition of vitamin D in cystic fibrosis. Addressing this issue is crucial in effectively and safely correcting vitamin D deficiency in CF.

Our study hypothesis is that CF patients with vitamin D deficiency exhibit altered pharmacokinetics of vitamin D and 25(OH)D when compared to non-CF subjects with vitamin D insufficiency or deficiency.

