2.0 OBJECTIVES AND PURPOSE

2.1 Primary Objective:

Characterize the pharmacokinetics of vitamin D3 and 25(OH)D3 with a single, high-dose of vitamin D3 in adults with CF.

Compare the pharmacokinetics of vitamin D3 and its metabolites between non-cystic fibrosis controls with low vitamin D levels and adults with cystic fibrosis

2.2 Secondary Objective:

Assess the anti-inflammatory effects of high dose vitamin D therapy in adults with CF.

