Appendix I: Study Calendar

Appendix I

	Screening	Day 0	Day 1	Day 7	Day 28	Day 56	Day 70
Informed Consent	X						
Medical History	X						
Medication History	X						
Height, weight	X						
Vital signs ^A	X	X	X	X	X	X	X
Safety labs ^B	X			X			
Pre-screening of 25OHD status	X						
PO drug administration		X					
Blood Pharmacokinetics (PK) ^C		X	X	X	X	X	X
Blood inflammatory biomarkers		X	X	X	X	X	X
Adverse Events		X	X	X	X	X	X

A. Vital signs to include blood pressure, heart rate, temperature, respiratory rate.

B. Safety labs to include comprehensive metabolic panel

C. All subjects will have a pre dose blood PK levels, 2, 4, 6, 8 hours and 1, 7, 28, 56, 70 days post dose of cholecalciferol. A 5mL serum separator tube will be used to collect the blood sample.

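### Does having only one sample between days 1 and 28 make the observed-Tmax comparison for 25(OH)D3 in section 13.1 unsound?

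*Combined protocol and SAP*

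**What the plan says.** Section 10.0 lists three primary outcome measures: Cmax, AUC and "Time taken to reach the maximum concentration". It does not say which analyte each refers to, but section 2.1 makes 25(OH)D3 a primary-objective analyte: "Characterize the pharmacokinetics of vitamin D3 and 25(OH)D3 with a single, high-dose of vitamin D3 in adults with CF". The comparison of CF with non-CF subjects is also a primary objective. The hypothesis at the end of section 1.0 is that "CF patients with vitamin D deficiency exhibit altered pharmacokinetics of vitamin D and 25(OH)D when compared to non-CF subjects" (the sentence goes on to define the comparators' vitamin D status).

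After the pre-dose sample, section 11.0 sets the draws "at 2, 4, 6, 8 hours and 1, 7, 28, 56 and 70 days after intervention". Note C of the study calendar in Appendix I agrees: "2, 4, 6, 8 hours and 1, 7, 28, 56, 70 days post dose of cholecalciferol". Section 3.0 describes a pilot with six CF and six non-CF subjects.

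Section 13.1 takes Cmax and Tmax from the measured concentrations: "The maximum concentration and time to maximum concentration will be determined from the observed data". It then sets the group comparison: "Differences in the pharmacokinetic parameters between non-CF controls and CF patients will be determined by non-parametric Wilcoxon-Mann Whitney test". It also plans a population analysis: "Multiple candidate models will be evaluated to identify the model that best describes the observed plasma concentration data for vitamin D3 and 25(OH)D3". It states no alpha, sidedness, power or decision rule, and does not say whether the rank test is exact or uses a tie-corrected normal approximation.

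**The concern.** An observed Tmax can only be one of the sampling times. Vitamin D3 itself has draws at 2, 4, 6 and 8 hours. A metabolite that peaks over days or weeks has only day 7 between day 1 and day 28. If most subjects in both groups peak somewhere in that stretch, nearly every 25(OH)D3 Tmax is recorded as 7 days and the rank test has almost nothing to rank. The trial could then report no difference in a primary outcome when formation of 25(OH)D3 is markedly slower or faster in CF, and a reader might count that against the hypothesis.

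A second worry is that, with so many ties, the exact and tie-corrected versions of the test can fall on opposite sides of 0.05, and the plan does not choose between them.

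**Working it through.** **Inputs from the protocol.** Sampling at 0, 2, 4, 6, 8 h and days 1, 7, 28, 56, 70 (section 11.0, Appendix I); 6 v 6 subjects (section 3.0); observed Tmax and Wilcoxon-Mann-Whitney (section 13.1). The protocol gives no power figure to reproduce.

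**Assumptions not in the protocol.** Two-sided 0.05; first-order formation (rate ka) and elimination (rate ke) of 25(OH)D3 above a constant baseline; half-life 10-40 days; between-subject CV of Tmax 30% or 60%; assay error 0-10%.

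**Step 1: which true peaks are recorded as day 7.** The rise above baseline is proportional to exp(-ke·t) - exp(-ka·t), and true Tmax = ln(ka/ke)/(ka - ke). Day 7 is the highest sample when C(7) exceeds both C(1) and C(28). For a half-life of 20 days, ke = ln 2/20 = 0.0347 per day.

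- C(1) = C(7) at ka = 1.706, giving Tmax = ln(1.706/0.0347)/(1.706 - 0.0347) = 2.3 days.
- C(7) = C(28) at ka = 0.1157, giving Tmax = ln(0.1157/0.0347)/(0.1157 - 0.0347) = 14.9 days.

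Over half-lives of 10-30 days the lower limit is 2.2-2.6 days and the upper limit 14.5-15.1 days. Without assay error, every true peak from about day 3 to day 14 is recorded as day 7.

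**Step 2: what the test needs if all 12 values are day 7 or day 28.** This step needs no assumption about peak times. With a and b subjects at day 28 in the two groups and k = a + b, the exact two-sided p is twice the hypergeometric tail when the test is against a more even split:

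- 0/6 v 4/6: 2 × C(6,4)/C(12,4) = 2 × 15/495 = 0.061
- 1/6 v 5/6: 2 × (36 + 1)/924 = 0.080
- 0/6 v 5/6 (and 1/6 v 6/6): 2 × 6/792 = 0.015
- 0/6 v 6/6: 2 × 1/924 = 0.002

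The tie-corrected approximation uses z = (|U - 18| - 0.5)/√V, with V = 3 × [13 - Σ(t³ - t)/132] and t the sizes of the tied sets.

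- 0/6 v 4/6: U = 30, V = 3 × (13 - 564/132) = 26.18, z = 11.5/5.117 = 2.25, p = 0.025
- 1/6 v 5/6: U = 30, V = 3 × (13 - 420/132) = 29.45, z = 11.5/5.427 = 2.12, p = 0.034

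The two versions disagree only when the counts differ by exactly four (0 v 4, 1 v 5, 2 v 6). A difference of three or less is non-significant under both, and five or more is significant under both.

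**Step 3: simulated power of the exact test, 6 v 6, Tmax CV 30%.**

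| True median Tmax (days) | Observed Tmax | True Tmax known |
|---|---|---|
| 5 v 10 | 0-1% | 92-94% |
| 7 v 14 | 4-8% | 92-95% |
| 10 v 20 | 23-58% | 92-94% |
| 5 v 20 | 55-85% | 100% |

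Ranges run over the assumed half-lives and assay errors. At CV 60% the exact test on observed Tmax reaches 1-3%, 7-8% and 13-17% for the three doublings, but knowing true Tmax would give only 42-46%. At that spread, six per group is itself a main limit.

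**Step 4: false positives.** With equal true medians of 7 days, the test on observed Tmax rejected in 0% of runs. The coarse scale costs sensitivity and does not create spurious differences.

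**The case for a change.** The case for a change is reasonable. The gap between day 1 and day 28 is a fact, Tmax is a primary outcome, and at CV 30% the grid rather than the sample size removes most of the power. At three splits the unstated version of the test decides significance. A few sentences would settle that, warn readers, and add a Tmax from the model already planned, with no new visits or samples. A misleading null in a pilot can also misdirect the next study.

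The arithmetic stands. The need for a change does not, for four reasons.

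- The loss depends on where 25(OH)D3 peaks, which the documents do not give. If the groups fall on opposite sides of about day 15, the test has useful power.
- Nothing in the protocol says a non-significant Tmax would be taken as evidence of equality. The hypothesis concerns pharmacokinetics in general. Cmax, AUC and the population model all bear on it, and the parameters compared under section 13.1 can include model rates that speak to timing.
- A caveat for one parameter of one analyte would single out a limit shared by every 6 v 6 comparison here.
- A fitted Tmax is not clearly better. It rests on the same sparse samples and on the chosen structural model. As an illustration, fitting a one-stage shape to two-stage data by individual least squares placed a 7-day median peak 3.4 days too late. That is not the planned population fit, so it shows only that the risk exists.

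The choice between exact and tie-corrected tests is a true omission, but a small one. With six per group and heavy ties an analyst would normally use the exact distribution and show how many subjects peaked at each visit. The splits in step 2 also assume nominal times. Actual draw times would break the ties without adding information.

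**Conclusion.** No change to the plan is needed. Observed 25(OH)D3 Tmax is coarse. If both groups peak between about day 3 and day 14, the planned comparison has roughly 0-8% power for a doubling that stays within that window (exact test, Tmax CV 30%, first-order kinetics). These figures rest on assumed peak times, half-lives and spreads; the sampling gap and the p-values for given splits do not. Taking Tmax from the data is a fair trade of sensitivity for freedom from a model, and the population analysis already in section 13.1 supplies the other view. What is left open, namely the version of the rank test, a count of subjects by sampling time, and ordinary caution about a null at 6 v 6, is reporting detail that a competent analyst will supply. A model-based Tmax may be shown descriptively if the team wishes.

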3.0 STUDY DESIGN

This is a pilot study to determine the pharmacokinetics-pharmacodynamics of vitamin D3 in CF patients. Clinically stable CF patients with a history of pancreatic insufficiency (n=6) and matching non-CF subjects (n=6) will be recruited in this study. The presence of pancreatic insufficiency will be based on a known CF genotype associated with pancreatic insufficiency. All subjects will be pre-screened for 25(OH)D status to include those with 25(OH)D levels below 30 ng/mL. The subjects will receive a single oral dose of vitamin D3, known as stoss therapy. The dose of stoss therapy will be based on patient's baseline serum 25-hydroxyvitamin D3 level. For CF patients, the dose will be administered with food and pancreatic enzyme supplement to maintain nutritional status. This dose was chosen because previous studies in pediatric CF patients demonstrated that a large single dose of up to 600,000 IU vitamin D3 raised and maintained sufficient 25(OH)D concentrations over 12 weeks without any signs of adverse events (25, 26).

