5.0 SELECTION AND WITHDRAWAL OF SUBJECTS

5.1 Inclusion Criteria (CF) :

Diagnosis of CF based on positive sweat chloride or known CF mutation
Patients with pancreatic insufficiency
Age \geq 18 years
Serum 25(OH)D concentrations below 30 ng/mL (75 nmol/L)

Inclusion Criteria (non-CF) :

Age \geq 18 years
Serum 25(OH)D concentrations below 30 ng/mL (75 nmol/L)

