6.0 STRATIFICATION/DESCRIPTIVE FACTORS/RANDOMIZATION SCHEME

6.1 Stratification factors: Not applicable

6.2 Descriptive factors. Not applicable

7.0 STUDY AGENT ADMINISTRATION OR INTERVENTION AND TOXICITY MANAGEMENT PLAN

7.1 Patients will be given a single dose, oral capsule of vitamin D3 based on measured 25-(OH) vitamin D level (25).

7.2 Drug studies:

AGENT	DOSE	ROUTE	DAYS	ReRx	NOTES
Cholecalciferol	600,000 IU	PO	1	Once	25-(OH) vitamin D \leq 25 nmol/L (\leq 10 ng/mL)
Cholecalciferol	500,000 IU	PO	1	Once	25-(OH) vitamin D 25-50 nmol/L (10-20 ng/mL)
Cholecalciferol	300,000 IU	PO	1	Once	25-(OH) vitamin D 50-75 nmol/L (20-30 ng/mL)

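### Vitamin D3 Cmax and AUC are compared between CF and non-CF with no account of a dose that varies up to two-fold: power is lost, and a reduction in CF could be masked

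*Combined protocol and SAP*

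**What the plan says.** - **Dose.** Section 3.0: "The dose of stoss therapy will be based on patient's baseline serum 25-hydroxyvitamin D3 level". Section 7.2 sets three tiers: 600,000 IU at or below 10 ng/mL, 500,000 IU at 10-20 ng/mL and 300,000 IU at 20-30 ng/mL.
- **Who can be in each tier.** Section 5.1 has the same entry limit for both groups, "Serum 25(OH)D concentrations below 30 ng/mL (75 nmol/L"), so every tier is open to both. Section 3.0 states that "matching non-CF subjects (n=6) will be recruited in this study", without naming a matching variable. Section 6.1 has "Stratification factors: Not applicable".
- **Outcomes.** Section 10.0 lists Cmax, Tmax and AUC as primary, with no reference to dose.
- **Analysis.** Section 13.1: "The maximum concentration and time to maximum concentration will be determined from the observed data". It does not say how AUC is obtained. A population model is planned ("Multiple candidate models will be evaluated to identify the model that best describes the observed plasma concentration data for vitamin D3 and 25(OH)D3"). The test between groups is "Differences in the pharmacokinetic parameters between non-CF controls and CF patients will be determined by non-parametric Wilcoxon-Mann Whitney test".
- **Objective.** The second primary objective in Section 2.1 is: "Compare the pharmacokinetics of vitamin D3 and its metabolites between non-cystic fibrosis controls with low vitamin D levels and adults with cystic fibrosis".

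**The concern.** Observed Cmax, and any AUC for the dose actually given, reflect dose as well as kinetics. Under this plan two subjects with identical kinetics can differ up to two-fold in vitamin D3 exposure because of their tier alone. That spread adds noise to a 6 versus 6 rank test. If the tiers also differ between the groups, dose is confounded with disease.

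Section 1.0 suspects low absorption of cholecalciferol in CF. A higher average dose in the CF group would work against detecting it.

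Tmax does not depend on dose under linear kinetics. The first primary objective, characterisation in CF, does not rest on this comparison.

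**Working it through.** The plan gives no alpha, power, effect size or variability, so there is no stated figure to reproduce.

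**Inputs from the protocol:** 6 CF and 6 non-CF subjects (Section 3.0), the three doses (Section 7.2), and an unadjusted Wilcoxon-Mann-Whitney test (Section 13.1). Dose ratios are 600/300 = 2.0, 500/300 = 1.67 and 600/500 = 1.20.

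**Assumptions, not in the protocol:** two-sided alpha 0.05; lognormal between-subject CV of 30, 50 or 70%; the tier mixes below; true CF/non-CF exposure ratio F at equal dose.

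**Test.** With 6 versus 6 there are 924 rank splits. Rejecting at U ≤ 5 or U ≥ 31 takes 38 of them, so the exact size is 38/924 = 4.1%.

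**Vitamin D3 model.** Exposure = F × dose^p × error, with log-scale SD = √ln(1 + CV²). There were 200,000 runs per cell and no pre-dose vitamin D3 term. Dose ratios are ratios of geometric means.

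Mixes:
- (a) CF one 600k, four 500k, one 300k; non-CF one 500k, five 300k. Dose ratio 1.45.
- (b) CF four 500k, two 300k; non-CF the reverse. Dose ratio 1.19.
- (c) Two per tier in each group. Dose ratio 1.00.

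Percent rejecting at CV 30/50/70%, p = 1:

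| Mix | F = 1, raw | F = 0.60, raw | F = 0.60, divided by dose |
|---|---|---|---|
| (a) | 26.5/14.9/10.5 | 4.3/4.3/4.2 | 71.6/34.3/20.7 |
| (b) | 3.7/4.3/4.3 | 17.5/11.4/8.8 | 71.6/34.2/20.8 |
| (c) | 0.5/1.7/2.5 | 34.2/21.2/15.0 | 71.4/34.3/20.8 |

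With F = 1, dividing by dose gives about 4% in every mix. In mix (a) the expected raw ratio with F = 0.60 is 0.60 × 1.45 = 0.87, which is why the reduction disappears. The raw rejections in mix (a) with F = 1 are almost all in the direction of CF higher (26.3/14.9/10.5%, against 0.0/0.0/0.1% for CF lower, in a separate run).

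**Tiers arising by chance.** If both groups are drawn from one tier distribution (10/45/45% or thirds for 600k/500k/300k), the dose ratio is at least 1.18 in either direction in 35% of studies and at least 1.44 in 2-3%. Averaged over draws, size is about 4%, and power at F = 0.60 is 42-43/25-26/18% raw against 71-72/34/21% normalised.

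**If exposure is less than proportional to dose**, mix (a), F = 1:
- p = 0.75: 18.8/10.5/7.8% raw, 6.2/4.8/4.6% normalised.
- p = 0.5: 11.4/7.1/5.8% raw, 11.5/7.2/5.8% normalised. The totals match but the direction reverses. At CV 30%, raw errors are almost all CF higher, while normalised errors are about 11.5% CF lower against 0.1% CF higher.

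**25(OH)D3 Cmax**, mix (a), no kinetic difference. Baseline was drawn within the tier limits (lower bound 4 ng/mL assumed), plus an assumed rise of 10-40 ng/mL per 300,000 IU; 100,000 runs per cell. Baseline moves opposite to dose, so the raw ratio runs from 0.91 to 1.17. False-positive rates over all CVs:
- Raw: 4-14%.
- Divided by dose with baseline left in: 9-47%.
- Baseline subtracted, then divided: about 4% only if the response is proportional and baseline is stable. With dose^0.5 it is 11-12/7/6%. With a 30% fall in the CF baseline and a 10 ng/mL rise it is 27/14/10%.

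**The case against.** **No tier mix is documented.** This stands. Both groups share one entry limit, and unnamed matching could include baseline 25(OH)D. A reader might infer from mix (a) that the planned test has a false-positive rate near 26%. The documents do not support that: inflation needs a systematic difference in tiers, a dose ratio of 1.19 produces none, and chance imbalance leaves average size near 4%. Nor would raw values falsely confirm low absorption if CF doses are higher, since the errors then point to CF higher. The power loss, by contrast, needs only a spread of doses. It vanishes if all subjects fall in one tier, and the largest spread is 1.67 rather than 2.0 if nobody is at or below 10 ng/mL.

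**The population model already takes dose as an input.** This is partly right. The parameters compared could include apparent clearance, which would account for dose. But Section 13.1 does not name it, takes Cmax from the observations, and leaves AUC open. A model-derived AUC for the dose given still carries dose.

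**Normalisation can create error of its own.** This stands as a limit. Nothing in the documents establishes proportionality from 300,000 to 600,000 IU. If exposure rises less than in proportion and CF doses are higher, dividing by dose moves errors towards CF lower, the direction the investigators expect.

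**It is a small pilot.** True, and at CV 70% power is only 21% even after normalising. The test still serves a primary objective, and a gain that needs no new data is worth having.

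**Conclusion.** The point holds, with limits, and should be fixed before the groups are compared. For vitamin D3, under proportional exposure, ignoring dose costs power even with identical tiers: 34/21/15% against 71/34/21% in mix (c). The harm becomes masking, with power near 4% in mix (a), only if CF subjects systematically receive higher doses. That is a possibility, not a documented fact. All sizes rest on the assumed CVs, true ratio, alpha and mixes.

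For 25(OH)D3 the direction is uncertain, and neither raw nor simply normalised values are reliable. A reader might conclude that a model-based CF effect should become the primary comparison for this analyte. The material does not support that: the route was not simulated, and a covariate effect estimated from 12 subjects will be imprecise.

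**What to change.** **Vitamin D3, Section 13.1.** Add, in substance: *The between-group test of vitamin D3 Cmax and AUC will use values from which any pre-dose concentration has been subtracted and which are then divided by the dose given. Raw values will be reported alongside by dose tier. Normalisation assumes dose proportionality, so a normalised difference will be interpreted together with the raw values within tiers.*

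**25(OH)D3, Section 13.1.** Keep the planned comparison. Report baseline-subtracted values by dose tier, and do not divide by dose unless baseline has first been removed. Add the CF effect from the planned population model, with dose as input and baseline modelled, as a supporting estimate with an interval.

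**Clarifications only.** State how AUC is obtained and over what interval, and name the matching variables in Section 3.0.

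**Cost.** A few sentences. Dose, the pre-dose sample and the model are already in the plan, so no new data are needed and dosing is unchanged. The price is the reliance on proportionality described above. Subtraction also assumes a stable baseline over 70 days, which is open to question because Section 7.4 bars vitamin D3 supplements during the trial while Section 1.0 cites a recommendation of 2,000 IU daily in CF. With 12 subjects over three tiers, the within-tier summaries will be thin and descriptive.

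### No CF versus non-CF effect estimate with a confidence interval is pre-specified; the primary between-group comparison rests on a 6 v 6 Wilcoxon test

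*Combined protocol and SAP*

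**What the plan says.** Section 2.1 lists two primary objectives. The first is to characterise PK in adults with CF. The second is comparative: "Compare the pharmacokinetics of vitamin D3 and its metabolites between non-cystic fibrosis controls with low vitamin D levels and adults with cystic fibrosis". The hypothesis in Section 1.0 has neither direction nor size: "CF patients with vitamin D deficiency exhibit altered pharmacokinetics of vitamin D and 25(OH)D when compared to non-CF subjects" with low vitamin D.

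Section 3.0 gives the size and status of the study: "Clinically stable CF patients with a history of pancreatic insufficiency (n=6) and matching non-CF subjects (n=6) will be recruited in this study", and "This is a pilot study to determine the pharmacokinetics-pharmacodynamics of vitamin D3 in CF patients". Section 10.0 names Cmax, Tmax and AUC as primary outcomes.

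Section 13.1 gives the analysis. It plans a population PK model and then a summary: "Patient demographics, clinical characteristics, and pharmacokinetic parameters will be summarized using descriptive statistics". The only method named for comparing the groups is the next sentence: "Differences in the pharmacokinetic parameters between non-CF controls and CF patients will be determined by non-parametric Wilcoxon-Mann Whitney test".

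Section 13 names no ratio, difference or shift for the PK comparison and no confidence interval. It gives no significance level, no target difference and no rule for reading a non-significant result. It does not say that the descriptive summary is by group, or that CF status enters the population model as an estimated effect.

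**The concern.** A rank test answers whether the two groups can be told apart. The second primary objective and the rationale need more. Section 1.0 argues that supplementation should be fitted to the individual's malabsorption and starting vitamin D status. That calls for the size of the CF effect on exposure and how uncertain it is.

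The gap bites in both directions. A significant result would come without a pre-specified size. A non-significant result would come without the range of ratios that the data still allow. At 6 v 6 that range may include large reductions, yet the plan makes the test the means of deciding whether a difference exists. A reader of the results could then take a p-value above 0.05 as evidence that CF does not alter PK.

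**Working it through.** The plan gives no power or precision figure to reproduce, so the check asks what a 6 v 6 comparison can show.

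**Inputs from the documents**
- 6 CF and 6 non-CF subjects (Section 3.0).
- Unpaired Wilcoxon-Mann-Whitney test (Section 13.1).

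**Assumptions, because the documents give no figure**
- Two-sided 5% level.
- Log-normal Cmax and AUC with the same CV in both groups. Section 1.0 says only that variability in response is wide, and that in a non-CF population. CVs of 40/50/60% are used as the main band, with 30%, 70% and 100% as sensitivity.
- No dropout and no ties.

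**Step 1: rejection rule.** There are 924 ways to split 12 ranks into 6 and 6. The smallest two-sided p is 2/924 = 0.0022. U = 5 gives p = 0.041 and U = 6 gives p = 0.065. The test therefore rejects only if U ≤ 5 or U ≥ 31 (of 36), and its actual size is 4.1%.

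**Step 2: precision of a ratio.** The log-scale SD is s = sqrt(ln(1 + CV²)). The t-based 95% CI for the geometric mean ratio is the estimate divided and multiplied by

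exp(t(0.975; 10) × s × sqrt(2/6)), with t = 2.228.

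At CV 50%: s = sqrt(ln 1.25) = 0.472, and the factor is exp(2.228 × 0.472 × 0.577) = 1.84.

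**Step 3: power.** Log-normal data were simulated and the Step 1 rule applied, with simulation error of about 1 percentage point or less.

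| Assumed CV | s | CI factor | 95% CI if observed ratio is 1.0 | Power, true ratio 0.7 | Power, 0.6 | Power, 0.5 |
|---|---|---|---|---|---|---|
| 30% | 0.294 | 1.46 | 0.69–1.46 | 42% | 72% | 93% |
| 40% | 0.385 | 1.64 | 0.61–1.64 | 26% | 48% | 74% |
| 50% | 0.472 | 1.84 | 0.54–1.84 | 19% | 34% | 56% |
| 60% | 0.555 | 2.04 | 0.49–2.04 | 14% | 26% | 44% |
| 70% | 0.631 | 2.25 | 0.44–2.25 | 12% | 21% | 36% |
| 100% | 0.833 | 2.92 | 0.34–2.92 | 9% | 14% | 22% |

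**Step 4: reading.** At CVs of 40–60%, a true 40% reduction in exposure is missed in about 52% to 74% of such studies (100 − 48 and 100 − 26). A true halving is missed in about 26% to 56%. As an illustration at CV 50%, an observed ratio of 0.6 has a CI of 0.6/1.84 = 0.33 to 0.6 × 1.84 = 1.10. The interval includes 1, but it also includes a two-thirds reduction. A bare p-value would not show that.

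**The case against.** The best defence is that this is a small pilot whose first aim is to characterise PK in CF, which needs no between-group test. A rank test is defensible at 6 v 6, and the same section plans other output. All of that stands, and it rules out several stronger readings that a reader might infer.

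- **That the trial yields only p-values and no estimate of size.** Section 13.1 plans descriptive statistics and a population PK model, and a crude ratio could be formed from group summaries. What is missing is a pre-specified between-group estimate with its precision.
- **That a non-significant result is the likely outcome even for a large difference.** This depends on the CV. For a halving, significance is the likelier outcome at a CV of 50% or less.
- **That a null result will be reported as unaltered PK.** The documents never say so. It is a risk against which the plan has no safeguard.
- **That six per group is itself an error.** The documents call the study a pilot and claim no power.

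The pilot label does not remove the gap. A study this small cannot test reliably, so its most useful comparative result is an estimate with an interval.

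**Conclusion.** The point holds as a gap in the planned analysis and reporting of a primary objective. Section 13.1 determines CF versus non-CF differences by a Wilcoxon-Mann-Whitney test and pre-specifies no between-group effect estimate with a confidence interval. The consequence is a risk of misreading a null result.

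Confidence is high that the interval is missing, because Section 13 can be read in full. The size of the risk is less certain, since it rests on assumed CVs. Across CVs of 30% to 100%, power for a halving runs from 93% down to 22%.

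**What to change.** In Section 13.1, beside the planned Wilcoxon test:

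1. For AUC and Cmax of vitamin D3 and of 25(OH)D3, report the CF/non-CF ratio with a 95% CI. Use either the geometric mean ratio from log values or the Hodges-Lehmann estimate on the log scale, and name one in advance.
2. For Tmax, report the Hodges-Lehmann difference with its CI. Tmax is read from the fixed sampling times in Section 11.0, so ties are likely and the interval method should allow for them.
3. Base the conclusion on the estimate and the range of ratios in the interval, never on non-significance alone. A fixed cut-off, such as calling a result inconclusive only if the CI includes 0.5 or 2, would not serve. The documents support no such margin, and at CV 40% an observed ratio of 1.0 has a CI of 0.61–1.64. That would escape the label while still allowing a reduction of more than a third.
4. Section 7.2 varies the dose from 300,000 to 600,000 IU with baseline 25(OH)D, so a raw ratio can mix dose with CF status. Report the dose distribution by group and a dose-normalised ratio as a sensitivity analysis. Normalising assumes that exposure is proportional to dose, so it should not replace the main estimate.
5. Section 3.0 calls the controls matching without naming the factors. State whether matching is by pair; if so, the estimate and test should reflect it.

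The cost is a revision of Section 13.1 and a little more analysis, with no added subjects or samples. The downside is that the intervals will be visibly wide.
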